## 11. CLINICAL ENDPOINTS COMMITTEE

A CEC will be constituted to adjudicate the following renal response (primary efficacy endpoint) parameters for subjects in this study:

- UPCR of  $\leq 0.5$  mg/mg, and
- eGFR  $\geq 60$  mL/min/1.73 m^2 or no confirmed decrease from baseline in eGFR of  $>20\%$ , and
- Received no rescue medication for LN (see Section 7.8, [Prohibited Therapy and Concomitant Treatment](#)), and
- Did not receive more than 10 mg prednisone for  $\geq 3$  consecutive days or for  $\geq 7$  days in total during Weeks 44 through 52, just prior to the renal response assessment

The CEC will adjudicate renal response by reviewing blinded data. Aurinia will establish a charter document explaining the working procedures and responsibilities of the CEC. All adjudication decisions of the CEC will be appropriately documented.

## **12. DATA AND SAFETY MONITORING BOARD PROCEDURES**

A DSMB will be constituted to protect the safety of study participants. The DSMB will receive blinded eCRF data in the form of tables and listings (prepared by an independent statistician), and review subject status changes and dosing decisions (where appropriate). Where appropriate, the DSMB may receive unblinded data (on a subject level or treatment group level) that should be reviewed in a closed session. The data should include, but is not limited to, demographics, subject enrollment, baseline characteristics, AE data, SAE data (by severity and causality), laboratory data, dose adjustments, protocol adherence, and subject withdrawals. The DSMB will evaluate the progress of the study, assess data quality and timeliness, participant recruitment, accrual and retention, and participant benefit versus risk. In addition the DSMB will monitor external factors relevant to the study, for example scientific and therapeutic developments that may affect participant safety or ethical status. Based on the observed benefits or adverse effects, the DSMB will make recommendations to Aurinia concerning continuation, termination, or modifications of the study.

Aurinia will establish a charter document explaining the working procedures and responsibilities of the DSMB. All deliberations and decisions of the DSMB will be appropriately documented.

## 13. STATISTICAL ANALYSIS

### 13.1 Statistical Methods

Complete details of the statistical and analytical methods will be provided in a formal Statistical Analysis Plan (SAP), which will be finalized prior to the database lock. A general description of the planned methods is provided below. Any deviation from the SAP will be noted and explained in the clinical study report.

### 13.2 Sample Size and Power Calculations

The total sample size will be 324 subjects (162 subjects per treatment arm). This is based on the following assumptions:

- A two group continuity corrected Chi square test with a 0.05 two-sided significance level will have 80% power to detect the difference between a placebo response rate of 20.0% and a Orelvo response rate of 34.4% (odds ratio=2.1) when the sample size in each group is 162 (total N=324).
- The effect of withdrawals will be investigated. Subjects withdrawing for any reason will be counted as non-responders in the primary analysis and therefore no adjustment of sample size for withdrawals is necessary.
- The impact of withdrawals on primary endpoint will be investigated with a tipping point analysis.

Table 3 shows the Orelvo response rates required to maintain a minimum 80% power at the planned sample size for given placebo response rates. These response rates all lead to odds ratios of around 2, which is a clinically relevant effect.

**Table 3 Orelvo Response Rates Required to Maintain a Minimum 80% Power**

Placebo Response Rate	Orelvo Response Rate	Odds Ratio
15%	28.4%	2.25
19%	33.2%	2.12
25%	40%	2.0

Note: Based on the planned sample size of 324 subjects (162 subjects per treatment arm).

### 13.3 Populations

#### 13.3.1 Intent-to-Treat Set

The intent-to-treat set will be based on intent-to-treat (ITT) principles and will consist of all subjects who are randomized to treatment. This group will be analyzed based on the treatment to which the subject was randomized.

### **13.3.2 Safety Set**

The safety set will consist of all randomized subjects who have taken at least 1 dose of study treatment. The subjects in this group will be analyzed based on the treatment they received. Subjects who receive treatment from more than 1 arm will be assigned to the Orelvo arm.

### **13.3.3 Per-protocol Set**

The per-protocol set will consist of all subjects eligible from the ITT population who do not have any major protocol violations. Major protocol violations will be defined in the statistical analysis plan and fully assessed at the subject level prior to unblinding of the study.

## **13.4 Background and Demographic Characteristics**

Demographic and clinical disease characteristics will be summarized by treatment arm in a descriptive manner but no statistical tests will be performed.

## **13.5 Study Treatment**

Compliance to the study treatment will be determined by dividing the number of softgel capsules taken by the expected number of softgel capsules to be taken (based on prescribed dose) over the subject's participation in the study.

Results will be summarized by means of descriptive statistics (n, mean, standard deviation, median, minimum, and maximum) and frequency tables, by treatment arm.

## **13.6 Concomitant Therapy**

All concomitant medications will be coded by the WHO Anatomical Therapeutic Chemical Drug Reference List classification. The version used will be provided in the clinical study report.

## **13.7 Efficacy Evaluations**

### **13.7.1 Primary Endpoint**

The primary endpoint is the number of subjects showing renal response at 52 weeks. Renal response at Week 52 will be adjudicated by the CEC based on the following parameters:

- UPCR of  $\leq 0.5$  mg/mg, and
- eGFR  $\geq 60$  mL/min/1.73 m^2 or no confirmed decrease from baseline in eGFR of  $>20\%$ , and
- Received no rescue medication for LN (see Section 7.8, [Prohibited Therapy and Concomitant Treatment](#)), and

- Did not receive more than 10 mg prednisone for  $\geq 3$  consecutive days or for  $\geq 7$  days in total during Weeks 44 through 52, just prior to the renal response assessment

Subjects who withdraw from the study prior to the Week 52 assessment will be defined as non-responders.

### **13.7.2 Secondary Endpoints**

#### **13.7.2.1 Key Secondary Endpoints**

- Time to UPCR of  $\leq 0.5$  mg/mg
- Partial renal response as defined by 50% reduction from baseline UPCR at Weeks 24 and 52
- Time to 50% reduction in UPCR from baseline
- Renal response at Week 52 (based on definition of primary endpoint)
- Duration of UPCR  $\leq 0.5$  mg/mg
- Proportion of subjects experiencing a confirmed  $>30\%$  decrease from baseline in eGFR at each timepoint

#### **13.7.2.2 Other Secondary Endpoints**

- Change from baseline in UPCR at each time point
- Change from baseline in serum creatinine, urine protein, and eGFR
- Change from screening in immunology parameters (C3, C4, and dsDNA) at Weeks 24 and 52
- Renal response with low-dose steroids (defined as renal response in the presence of corticosteroids of  $\leq 2.5$  mg/day between Weeks 16 to 24 and Weeks 44 to 52)
- Change from baseline in HRQoL at Weeks 12, 24, and 52
- Health Resource Utilization at Weeks 24 and 52
- Change from baseline in the SELENA-SLEDAI Index score at Weeks 24 and 52

## 13.8 Statistical and Analytical Methods

### 13.8.1 Primary Efficacy Analysis

The primary efficacy endpoint is the renal response at Week 52 (Section 13.7.1, [Primary Endpoint](#)).

The study null hypothesis  $H_0$  and alternative hypothesis  $H_1$  are as follows:

$H_0$ : There is no difference in renal response between Orelvo and placebo.

$H_1$ : There is a difference in renal response between Orelvo and placebo.

The null hypothesis  $H_0$  will be rejected in favor of  $H_1$  if there is evidence at the 5% significance level using a 2-sided test.

The primary efficacy analysis will be conducted on the ITT set using logistic regression with terms for treatment, baseline UPCR, biopsy class, and MMF use at baseline. The results being expressed as an odds ratio (and associated two-sided 95% CI) for Orelvo compared to placebo. Odds ratios greater than unity show the odds of response are greater for Orelvo than for placebo and therefore indicate a benefit of the Orelvo treatment arm.

### 13.8.2 Sensitivity Analyses

The following sensitivity analyses will be performed:

- Renal response at Week 52 will be analyzed using a logistic regression including only a term for treatment. This analysis will be performed on the ITT set.
- The analysis described in Section 13.8.1, [Primary Efficacy Analysis](#) will be repeated for the per protocol analysis set.
- The impact of withdrawals on primary endpoint will be investigated with a tipping point analysis.

### 13.8.3 Secondary Efficacy Analysis

All the secondary efficacy analyses will be performed on the ITT set.

#### 13.8.3.1 Response Endpoints

The following secondary endpoints will be analyzed using logistic regression as outlined in Section 13.8.1, [Primary Efficacy Analysis](#). These analyses will be conducted on the ITT population and will incorporate baseline variables within the model as appropriate.

- Renal response at Week 52 (based on definition of primary endpoint)

- Partial renal response as defined by 50% reduction from baseline in UPCR at Weeks 24 and 52
- Renal response with low-dose steroids (defined as renal response in the presence of corticosteroids of  $\leq 2.5$  mg between Weeks 16 to 24 and Weeks 44 to 52)

### **13.8.3.2 Time to Endpoints**

The following secondary endpoints: time to renal response, time to partial renal response, and duration of UPCR  $\leq 0.5$  mg/mg will be analyzed by comparing the survivor function between treatment arms. It will be estimated using Kaplan-Meier methodology and will be presented as a plot showing a line for each treatment group. Median time-to-event along with two-sided confidence intervals will be displayed.

Cox's proportional hazards model will be performed to assess the significance of the differences between treatment arms. The model will include terms for treatment, baseline UPCR, biopsy class, and MMF use at baseline. Estimates of the treatment effects will be expressed as hazard ratios (and associated 95% CI) for Orelvo relative to placebo. Hazard ratios greater than unity show the hazard to be greater for Orelvo than for placebo and therefore indicate that the events in question generally occur earlier on active Orelvo.

The log-rank test and Cox's proportional hazards model assume that the hazard ratio is constant over time. This assumption will be checked graphically by plotting log-log survivor functions for the treatment groups. It should be noted that modest deviations from the proportionality assumption generally will not invalidate inference.

### **13.8.3.3 Change from Baseline Endpoints**

The following secondary endpoints will be analyzed using a Mixed Effect Model Repeated Measures analysis with treatment arm, visit, treatment by visit interaction, biopsy class, and MMF use at baseline included as a covariate in the model. Results will be expressed as differences between treatment arms (along with the associated 95% CI).

- Change from baseline in UPCR at each visit
- Change from baseline in serum creatinine, urine protein, and eGFR at each visit
- Change from screening in immunology parameters (C3, C4, and anti-dsDNA) at Weeks 24 and 52
- Change from baseline in HRQoL at Weeks 12, 24, and 52
- Change from baseline in the SELENA-SLEDAI score at Weeks 24 and 52

#### **13.8.3.4 Health Resource Utilization**

- Health Resource Utilization at Weeks 24 and 52. Key aspects will be summarized by visit and changes over time will be explored.

#### **13.8.4 Multiplicity**

An overall type 1 (false-positive) error rate of 5% for the efficacy endpoints will be maintained so that no statistical significance for the secondary efficacy endpoints will be claimed unless the principal analysis of the primary efficacy endpoint using the ITT set is statistically significant at the 5% level. The Hochberg step-up method will be used to adjust for multiple comparisons amongst key secondary endpoints and maintain the overall type 1 error rate [21]. Data from all analyses, regardless of the level of significance, will be presented for review.

### **13.9 Safety Evaluations**

Specific safety endpoints are as follows:

- Biochemical (including liver function tests) and hematological laboratory tests
- AE profile and routine biochemical and hematological safety parameters
- Vital signs (BP, HR, temperature) at specific time points and change from baseline
- Standard 12-lead ECGs change from baseline
- Discontinuations from treatment
- Concomitant medications

Laboratory values, vital signs, and other safety parameters providing numeric data will be summarized by treatment arm, visit, and as change from baseline.

Adverse events will be coded using the latest available version of the Medical Dictionary for Regulatory Activities, the version of which will be provided in the clinical study report.

Treatment-emergent adverse events will be summarized by treatment arm, system organ class, and preferred term. SAEs, SAEs that led to death, and SAEs/AEs that led to withdrawal will also be summarized and listed.

Only AEs which started on or after the date of first dose of study treatment will be considered TEAEs, though all AEs after informed consent will be recorded. SAEs occurring at any time after informed consent will be summarized. All concomitant medications will be summarized.

Details of these and other analyses will be provided in the SAP.

All study data analyses involving laboratory values will be based on results from the central laboratory.

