  - 3 Subjects who do not enroll into the continuation study will have a follow up safety visit 4 weeks after the last dose of study treatment.
  - 4 If a subject has not had a recent kidney biopsy, one may be performed to assess eligibility for the study provided informed consent has been given and results are received prior to randomization. If one is performed as part of standard of care after randomization, the results will be recorded in the electronic case report form.
  - 5 Complete physical examination at screening, abbreviated examination at all other applicable visits. Height is measured at screening only.
  - 6 During the study, and after screening, in the event that a subject is noted to have a QTcF value exceeding 500 msec, or >60 msec more than baseline, the ECG will be repeated; see Section 9.1.4.1, [Procedures to Manage a Treatment-Emergent Increase in QTc](#). Electrocardiograms will be recorded digitally after the subject has been in a resting, supine position for at least 5 minutes.
  - 7 Week 12 only.
  - 8 Laboratory assessments will be performed according to the schedule in Section 9.1.1, [Laboratory Assessments](#); subjects must be fasting for at least 8 to 12 hours at baseline and end of study/early termination.
  - 9 Blood samples will be collected at 0 and 2 hours post dose for pharmacokinetics.
  - 10 Two FMV specimens, to be performed and resulted before baseline.
  - 11 24-hour urine collection should begin 2 days prior to the scheduled study visit in order not to coincide with the FMV sampling due on the day of the study visit.
  - 12 Serum pregnancy test to be evaluated at central laboratory at screening, Week 24, and Week 52; urine pregnancy test will be performed locally at all other applicable visits.
  - 13 Adverse events will be recorded after the subject signs the ICF; AEs which occur during screening or prior to the first dose of study treatment will not be considered TEAEs.
  - 14 Concomitant medications include all herbal medicines and supplements taken by the subject.
  - 15 For details on HRQoL assessments, see Section 9.3.1, [Health-related Quality of Life Assessments \(HRQoL\)](#).
  - 16 For details on Healthcare Resource Utilization, see Section 9.3.2, [Healthcare Resource Utilization Assessment](#).
  - 17 Compliance only.
  - 18 All scheduled procedures must be done prior to first dose, including IV methylprednisolone and MMF.

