### **10.2 Adverse Event Descriptors**

#### **10.2.1 Intensity/Severity Categorization**

The term "severe" is often used to describe the intensity (severity) of a specific event (as in mild, moderate, or severe myocardial infarction); however the event itself may be of relatively minor medical significance (such as severe headache). This is not the same as "serious," which is based on subject/event outcome or action criteria usually associated with events that pose a threat to a subject's life or functioning. Seriousness (not severity) serves as a guide for defining regulatory reporting obligations.

In general, the intensity of a particular AE to be recorded is the worst intensity experienced by the subject during the course of the event. The medical assessment of intensity will be determined by using the following definitions:

- Mild: The AE is easily tolerated and does not interfere with usual activity.
- Moderate: The AE interferes with daily activity, but the subject is still able to function.
- Severe: The AE is incapacitating and the subject is unable to work or complete usual activity.

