#### **10.2.4 Symptoms of the Disease Under Study**

Symptoms of the disease under study will not be classed as AEs as long as they are within the normal day-to-day fluctuation of the disease. An explanation of these circumstances must be written in the source documents.

Worsening of the symptoms however, will be recorded as an AE, and clearly marked as worsening or by the subject's worst observed intensity.

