#### **10.2.5 Clinical Laboratory Evaluations**

A change in the value of a safety laboratory investigation can represent an AE if the change is clinically relevant in the opinion of the Investigator or if, during treatment with the study treatment, a shift of a parameter is observed from a normal value to a pathological value, or a further worsening of an already pathological value.

If, at the end of the treatment phase, there are pathological laboratory values which were not present at baseline, further clinical or laboratory investigations will be performed until the values return to within reference range or until a plausible explanation (e.g., concomitant disease) is found for the pathological laboratory values.

If the Investigator considers such an AE as serious it must be reported as an SAE.

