### **10.3 Reporting Procedure for AEs, SAEs, and Pregnancy**

#### **10.3.1 Adverse Events**

All AEs either observed by the Investigator or one of his/her medical collaborators, or reported by the subject spontaneously, or in response to a direct question, will be noted in the AE section of the subject's eCRF and source documentation. This applies to all AEs regardless of presumed relationship to the study treatment. Adverse events leading to discontinuation of study treatment must be collected.

If any AE is reported, the date of onset, relationship to study treatment, any action taken, date of resolution (or the fact that it is still continuing or has become chronic), outcome, and whether the AE is serious or not, will be recorded. Use of colloquialisms and abbreviations should be avoided. Only 1 AE term should be recorded in the event field on the AE eCRF. Where possible, the Investigator should report a diagnosis rather than signs and symptoms or

abnormal laboratory values. However, if a constellation of signs and/or symptoms cannot be medically characterized as a single diagnosis or syndrome at the time of reporting, each individual event should be recorded on the AE eCRF. If a diagnosis is subsequently established, all previously reported AEs based on signs and symptoms should be nullified and replaced by one AE report based on the single diagnosis, with a starting date that corresponds to the starting date of the first symptom of the eventual diagnosis.

The AE reporting period begins at the time the ICF is signed by the subject. The AE reporting period ends at Visit 15 (if the subject participates in the continuation study) or the study follow-up visit (Visit 16), if the subject does not participate in the continuation study. Adverse events persisting at the time of study completion will be followed by the Investigator through contact with the subject until resolution or stabilization has occurred (or the subject is lost to follow-up and cannot be contacted) and recorded in the source documents. If the subject reports an AE, it is the Investigator's responsibility to acquire sufficient information in order to assess causality. This may require additional laboratory testing, physical examinations, telephone contacts, etc. In circumstances where the Investigator is unable to make contact with the subject, the Investigator must provide a written statement to Aurinia confirming that the subject is lost to follow-up.

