### 6.13.1 Adverse Events

A treatment emergent adverse event (TEAE) is defined as:

- Any AE that has an onset on or after the first dose of study drug up to last dose + 30 days. For subjects consenting to the AURORA 2 continuation study there will be an additional constraint to the TEAE definition: events must have an onset date prior to the first dose of AURORA 2 study drug.

A treatment-related TEAE is defined as a TEAE that is assessed by the Investigator or Sponsor as being related to study drug. If a TEAE has a missing relationship to study drug it is assumed to be related to the study drug for analysis purposes.

A disease-related TEAE is defined as a TEAE that is assessed by the Investigator or Sponsor as being related to the disease under study. If a TEAE has a missing relationship to the disease under study it is assumed to be related to the disease under study for analysis purposes.

Missing severity assessments will be summarised as severe.

The following tables will be presented for AEs:

- Summary table of overall incidence, the number of events, risk difference and 95% CI (voclosporin-placebo) including the following top line summaries:
  - Any AE
  - Any TEAE
  - Any Treatment-Related TEAE
  - Any Serious TEAE
  - Any Treatment-Related Serious TEAE
  - Any TEAE Leading to Voclosporin/Placebo Discontinuation
  - Any TEAE Leading to Death
  - Treatment-Related TEAE Leading to Death
  - Disease-Related TEAE
  - Disease-Related Serious TEAE

Detailed list of AE tables is given at the end of this SAP.

In counting the number of AEs reported, a continuous event (i.e., reported more than once and which did not cease), will be counted only once for a subject; a non-continuous AE reported several times by the same subject will be counted as multiple events.

Additional tables for serious TEAEs will be provided for each of the four regions: North America, Latin America, Europe/South Africa and Asia Pacific. Similar tables will also be provided for serious TEAEs occurring between day 1 and day 84 (Up to week 12), day 85 to day 168 (Week 12 to 24) and greater than day 168 (after week 24).

All AEs will be listed and a glossary of unique verbatim terms with coding information will be provided.

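### TEAE status rests on onset date alone, so some pre-dose events that worsen on drug miss the SAP's serious, discontinuation and death comparisons

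*Protocol*

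**What the plan says.** Three places define a TEAE, all by onset.

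- Protocol 13.9: "Only AEs which started on or after the date of first dose of study treatment will be considered TEAEs".
- Protocol Schedule of Events, footnote 13: "AEs which occur during screening or prior to the first dose of study treatment will not be considered TEAEs".
- SAP 6.13.1: "Any AE that has an onset on or after the first dose of study drug up to last dose + 30 days". For subjects entering the continuation study, onset must also precede the first dose there.

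Three rules govern how events are recorded and counted.

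- Protocol 10.2.1, in a sentence qualified as general: "the intensity of a particular AE to be recorded is the worst intensity experienced by the subject during the course of the event".
- Protocol 10.3.1: when symptoms are later given a diagnosis, the symptom records are replaced by one record, "with a starting date that corresponds to the starting date of the first symptom of the eventual diagnosis".
- SAP 6.13.1: "a continuous event (i.e., reported more than once and which did not cease), will be counted only once for a subject".

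Two provisions do address worsening. Protocol 10.2.4, on symptoms of lupus, says: "Worsening of the symptoms however, will be recorded as an AE, and clearly marked as worsening". Protocol 10.2.5 lets a laboratory change on treatment be an AE when it is a shift from normal to pathological, "or a further worsening of an already pathological value".

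Protocol 13.9 also promises summaries of SAEs at any time after consent, of SAEs that led to death, and of SAEs or AEs that led to withdrawal. None of these is limited to TEAEs.

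**The concern.** AE collection starts at consent, so there is a pre-dose period in which an event can begin. If that event then gets worse on study drug, the worsening is on-treatment safety information, but the definition classifies the event by when it began.

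The two worsening provisions cover lupus symptoms and laboratory values. They do not cover a non-lupus infection, a gastrointestinal event or hypertension. Protocol 1.2.5 names Infections and Infestations, Gastrointestinal Disorders and Vascular Disorders as the classes in which TEAEs rose over placebo and with dose.

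At stake is whether the by-arm comparisons most likely to be read for safety (serious events, discontinuations, deaths) contain every event that became serious or fatal on drug.

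**Working it through.** The plan states no figure on this point, so there is none to reproduce. The check sets the rules side by side and follows one hypothetical event through them.

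**1. Window in which a pre-dose event can start.** Protocol 14.1 allows consent up to 30 days before Visit 1. Protocol 9.2.1 places Visit 1 within 30 days before Day 1. AE reporting begins at consent (Protocol 10.3.1). The window is at most 30 + 30 = 60 days.

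**2. One event through the recording rules.** Suppose a cough, not attributed to lupus, is recorded in screening, diagnosed as pneumonia on Day 10, and proves fatal.

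- Protocol 10.3.1: the cough record is replaced by a single pneumonia record dated to the start of the cough, which is before dosing.
- Protocol 10.2.1: that record carries the worst intensity reached.
- Protocol 13.9 and SAP 6.13.1: onset precedes first dose, so it is not a TEAE.
- Protocol 10.2.4 and 10.2.5 do not apply, because it is neither a lupus symptom nor a laboratory value.

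**3. Where that event appears in the planned outputs.**

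| Output | Source | Event included? |
|---|---|---|
| Row for any AE, with risk difference and 95% CI | SAP 6.13.1 | Yes |
| Rows for serious events, discontinuation and death, same table | SAP 6.13.1 | No, TEAE only |
| Serious events by region and by study period | SAP 6.13.1 | No, TEAE only |
| Two exposure-adjusted incidence tables | SAP 6.13.1.1 | No, TEAE only |
| Summaries of SAEs, fatal SAEs, and SAEs/AEs leading to withdrawal | Protocol 13.9 | Yes |
| Listing of all AEs | SAP 6.13.1 | Yes |

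The table also shows the mismatch between the documents: Protocol 13.9 summarises SAEs from consent onwards, while every serious or fatal row named in SAP 6.13.1 is restricted to TEAEs. SAP Section 9 does not list this as a change from the protocol.

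**4. Whether it can be repaired at analysis.** The items that Protocol 10.3.1 says are recorded are onset date, relationship, action taken, resolution date, outcome and seriousness. A date of worsening, or of becoming serious, is not among them. Unless the eCRF holds more than this list, a worsening rule could not be applied reliably from the data afterwards.

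**5. Size per subject.** The documents give no count of such events. Assuming 162 treated per arm (the planned number randomized), omitting k subjects from one arm changes its incidence by 100 × k/162 percentage points:

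- k = 1: 100 × 1/162 = 0.62
- k = 3: 100 × 3/162 = 1.85
- k = 5: 100 × 5/162 = 3.09

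The values of k are illustrations only.

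**The case against.** The strongest reply is that little is actually hidden. The any-AE row gives a formal arm comparison that includes these events. Protocol 13.9 commits to summaries of SAEs, fatal SAEs and withdrawals with no TEAE limit, so the fatal pneumonia in the example would be reported there. SAP 6.4 tabulates withdrawals with reasons, and study drug discontinuations, by arm whatever the TEAE status. All of this stands. It rules out the stronger inference that such events disappear from every arm comparison. It does not close the gap, because the any-AE row mixes all severities and cannot show a difference in serious or fatal events.

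Second, the recording rules are less rigid than they look. Protocol 10.2.1 says which intensity to record; it does not forbid a new record when an event worsens. Worsening of lupus symptoms and laboratory values can enter as new AEs. Completely missing start dates of events that are ongoing or stop after first dose are imputed to first dose (SAP 6.2.6), which favours TEAE status. This stands too. What remains is non-lupus, non-laboratory events with a known pre-dose start, for which no rule says whether worsening opens a new record.

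Third, carry-in is limited by eligibility: current infection requiring IV antibiotics is an exclusion, as is any condition judged to raise risk (Protocol 5.3). This makes the problem rarer but does not remove it.

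Fourth, SAP 6.2.15 on adverse events and the table list in SAP Section 11 were not available for this review. A derivation rule on worsening, or a separate all-SAE table by arm, cannot be excluded. The point therefore rests on SAP 6.13.1 as written.

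**Conclusion.** The point holds in a limited form. In both documents a TEAE is defined by onset alone. A non-lupus, non-laboratory event that starts between consent and first dose and worsens on drug, including one back-dated under Protocol 10.3.1, falls outside the TEAE tables and outside the SAP's named by-arm comparisons of serious events, discontinuation, death and exposure-adjusted incidence. Separately, the SAP's visible serious and fatal rows do not match the all-SAE summaries in Protocol 13.9.

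The total size is not derivable from the documents; only the step of about 0.6 percentage points per omitted subject is, assuming 162 treated per arm.

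A reader might go further and infer that the comparison is biased towards no difference because more such events would be omitted on voclosporin. That is plausible but not shown: it needs carry-in and worsening rates by arm, and the documents give none. Nor do the Phase 2 deaths (10 on the low dose, 1 on placebo, Protocol 1.2.4.2) support it, since nothing says that any of them arose from an event that began before dosing. This is an inexpensive improvement to the definition, not a demonstrated distortion of the safety results.

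**What to change.** 1. In Protocol 13.9, Schedule of Events footnote 13 and SAP 6.13.1, extend the TEAE definition to AEs with onset before first dose that increase in severity, become serious, or lead to discontinuation or death on or after first dose, with the same end of window as now.
2. Instruct sites to enter such a worsening as a new AE record with its own date. When a diagnosis replaces pre-dose symptoms under Protocol 10.3.1, keep the date of worsening or diagnosis as well. State in SAP 6.13.1 how the rule that counts a continuous event once applies to these records.
3. Add by-arm rows for all post-consent SAEs and all deaths to the SAP's overall table, so that it matches Protocol 13.9. If Section 11 already contains such tables, a cross-reference is enough.
4. SAP 6.11.1 lets a failing eGFR count against response only when a related, eGFR-associated TEAE is present. State whether the extended definition applies there, so that the primary endpoint does not change by accident.

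The cost is protocol and SAP wording, a change to the eCRF completion guidance, and slightly more TEAEs in both arms.
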